## **F. Sources of research data**

The source of research data is clients' (injection drug users) biological specimens and their self-reported survey data (all clients); and the qualitative interview (for people who complete this activity). Provider participant data will be limited to their qualitative interview and quantitative mail and email-based survey. For phase two we will also be collecting demographic information, program data from intervention sessions (upon completion of the study), testing data, and contact information from all participants.

*DHS Linkage Study on COVID-19 Pandemic Impact Among UG3 Participants.* For this analysis, we will obtain external data from Wisconsin DHS via linkage of identifiable data from UG3 participants will several DHS registries, as described in detail above.

## **G. Potential risks**

Potential psychological risks to participants in this study are: (1) negative consequences if confidentiality of information obtained in this study were violated; (2) embarrassment, discomfort, or distressed emotional reactions to the study assessment measures; (3) increased anxiety about personal safety and wellness resulting from the interview or survey; and (4) potential for minor bruising or irritation from a phlebotomy blood draw if confirmatory HIV test is required due to a

reactive rapid test. Emotional distress is common after a person learns he or she is HIV or HCV-positive.

**COVID-19 Response.** In addition to the above risks, if a participant may go into the community for treatment, confirmatory testing, or any other reason related to the study there is a risk of COVID-19 transmission. In order to mitigate this, Vivent Health is providing as many virtual services at possible, at home testing, and referrals to tele-medicine sources when available.

## **H. Steps to protect against or minimize potential risks**

**Confidentiality protections.** A number of steps will be taken to protect the confidentiality of participants' data and their identity. All investigators have extensive experience in the safe collection, handling, and storage of sensitive and highly confidential data. All name-identified information (e.g., informed consent) will be kept in a locked file, separate from any data. Data-related materials will be identified by a unique Research Identification Number (RIN) and stored in a second locked file. All materials will be kept in a locked room, ensuring two locking measures. Access to these two files will be limited to the research team. All data files will be securely transferred using encryption. Computer databases will be password protected and accessible only to the research team. No individual identities will be used in any reports or publications that may result from this research project. Data requested from researchers from organizations not formally collaborating on this research project will only be shared in aggregate form per NIH and federal data sharing regulations.

Prevention Navigation materials will utilize study ID only, and will not include a name on them, as to prohibit this link from being made again in another location and to protect the individual's identity should a breech occur. Navigation files will be double locked and stored separately from any forms containing the participant's name if a physical copy. All virtual copies will be stored in a secure Vivent Health server. Because of the nature of the participant's lives, navigation sessions may need to occur outside of the office in a public location. Only essential documents will be brought with the navigator in a locked binder with a secure code. Documents will be immediately returned to the office to be double locked and stored properly. Should a prevention navigator need to work from home (for example, due to COVID-19 restrictions) essential files with study IDs and not names may be brought home in a secured binder and locked in a secure location inside their home. Files may not be left in a vehicle or outside of a locked room or cabinet.

We recognize that we are asking participants to provide sensitive information about private behavior and health. Our research team is experienced in the collection of this type of information, and we will implement multiple safeguards to protect participants' confidentiality. All project protocols will be subject to review by the institutional IRB at the University of Wisconsin-Madison. The UW-Madison IRB will approve research involving children only if the IRB finds that the research includes any required additional safeguards outlined in ethical principles and applicable federal regulations, state laws and institutional policies. An inter-institutional agreement will be signed between the University of Wisconsin-Madison and Tulane University for IRB oversight; and a data sharing agreement will be obtained for any information shared with the Wisconsin Department of Health Services AIDS/HIV

Program, the Wisconsin Division of Care and Treatment Services, and any outside jurisdictions (e.g., GHOST lab) with which data will be shared. Vivent Health staff will be included in the University of Wisconsin-Madison IRB protocol. A Certificate of Confidentiality has been obtained as a condition of the NIH grant award. All study participants will be fully informed of the project goals and procedures, and of their rights as research participants, including the right to not participate without penalty. Signed consent will be obtained prior to the collection of any data, or the conduct of any research activities.

Pregnant women are a vulnerable population whose inclusion in this research is justified by the increasing incidence of neonatal abstinence syndrome, and increased prevalence of opioid use among women of childbearing age. Although drug use in pregnant women does not require mandatory reporting under state law, study team members may choose to voluntarily report it. The possibility of this and the risks if this were to be reported will be clearly outlined in the consent form. Prevention navigators will also communicate with the participant the risk of medical providers reporting such drug use when initiating referrals for care.

Per HIPAA, participants will be advised during the consent process of our intent to collect biological specimens to test for HIV, HCV, and other STIs. Positive tests will be reported to the health department per state and local regulations.

Follow up contacts will be performed with participants in both the intervention and control groups. Vivent Health study staff will perform all follow up contacts with intervention participants. These follow ups include appointment reminders, appointment scheduling, checking in after an important appointment, booster sessions via phone, and discussing test results. These contacts will be made in accordance to the participants' preferred contact method. Contacts with the control group will all be performed by the project manager on the designated study phone to enhance trust with participants who may not want calls from strangers. Calls will be made to remind them to schedule follow up visits. Control participants will be called no more than 3 times between each research visit to eliminate disruption to their daily lives. All social media interactions will occur using a professional Facebook account separate from personal accounts. Facebook's privacy policy will be given to the participant if they choose to contact their PN via Facebook, and they will be reminded that it is not a secure form of communication. PNs will suggest alternative ways to privately discuss treatment and care in detail. All phone calls and text messages performed by Vivent Health staff will be done on a Vivent Health provided work phone, separate from staff's personal information. These phones have secure codes and laptops have two-factor authentication. Phone calls and text messages sent by the UW research team will be performed on a study phone only accessed by one person with a secure code. No names will be stored in the phone.

*DHS Linkage Study on COVID-19 Pandemic Impact Among UG3 Participants.* Given the transient nature of people who inject drugs, re-consenting participants for this data linkage study and analysis would not be feasible, as the proposed analysis will occur at least two years after original recruitment of UG3 participants when contact information is no longer valid. Moreover, the need for this analysis stems from the COVID-19 pandemic emergency, which was not foreseeable at the time of original recruitment. As such, we will carry out the linkage via a waiver of consent and partial waiver of

authorization. Identifiable information that will facilitate the linkage will be shared within the purview of Data Use Agreements that will be established prior to any data transfers. Study activities for this data linkage have been reviewed and approved by the Data Governance Board at DHS, pending subsequent IRB approval and the establishment of the aforementioned agreements. Once the linkage is completed, participant data will be destroyed and not kept on file by DHS. Our study team will receive the linked dataset containing only a unique research identification number (identifiers will be removed before DHS provides the linked dataset).

**Steps to reduce discomfort or anxiety resulting from study participation.** Assessment measures involve sensitive topics related to safety and wellness. Some participants may feel awkward or embarrassed when discussing, hearing about, or being asked to provide information related to their safety and wellness. Staff are trained to employ techniques that prevent, reduce, or minimize embarrassment, discomfort, or atypical stress associated with study participation. Staff will be trained to observe for any evidence that a participant may be overly anxious and to assess whether threat sensitization and vulnerability perceptions are realistic. Vivent Health and research field staff will be required to have extensive research- or program-based experience with the conduct of HIV-related research. The project will be guided by a detailed procedural manual, and field staff will receive intensive training focused on the specific project protocols and materials to ensure that they are being rigorously and consistently implemented, including extensive role-play rehearsal of recruitment, enrollment, and consent procedures and assessment procedures and materials. Staff will be required to demonstrate competence with project protocols prior to implementation. Investigators and field staff have or will be required to complete the NIH required CITI web-based ethics training. Interviews will be supervised by the lead project investigators to ensure protocol adherence. The field team will meet regularly to discuss implementation issues and areas warranting additional training. If research personnel change during the course of the study, new staff will be required to complete the training described above prior to conducting any research activities.

**HIV, HCV, and syphilis testing and counseling safeguards.** All testing staff have completed the Wisconsin AIDS/HIV Program state HIV test counselor training to ensure that HIV pre- and post-test counseling is conducted in accordance with state guidelines. Testing staff will be further required to complete training and demonstrate competence with the fingerstick collection of whole blood specimens (i.e., rapid HIV, HCV, and syphilis point-of-care testing methodology) and phlebotomy blood draws prior to study Implementation; and complete annual training in blood borne pathogen control ("universal precautions") to ensure adherence to the Occupational Safety and Health Administration Occupational Exposure to Blood borne Pathogen standards. Any new staff who are hired will be required to complete the training package described above, and demonstrate competency with HIV, HCV, and syphilis testing and counseling. [name]., will provide on-going review of counseling and testing procedures, as well as the interpretation and provision of test results to study participants. If any adverse physical harm results from the administration of the rapid HIV, HCV or syphilis tests, free medical follow-up will be provided to participants. Vivent Health is a CLIA-certified HIV test site funded, in part, by the Wisconsin Division of AIDS/HIV's HIV testing program.

Specimens will only be sent for confirmatory testing for those rapid tests that they are already positive for, therefore, no new health information will be generated by analysis of these samples.

**COVID-19 Pilot.** All data collected from participants will be stored on a secure server, REDCap, Qualtrics, and/or Client Point. Participants will be assigned a unique study ID, which will be linked to their name in on the screening form, housed on the Vivent Health server, PHI box, and REDCap. All other forms used for these participants will only have their study ID attached. Testing forms will follow Vivent Health's virtual testing protocol.

All calls for virtual navigation, and originally proposed UH3 navigation performed virtually, will be conducted through a cell phone provided by UW or Vivent Health, or on Vivent Health's approved video conferencing platform, Microsoft teams. Staff may conduct reminders or follow ups via their work telephone. Facebook messenger from a business profile, or mail if the client consents to that form of contact.

All other privacy and protection safeguards listed in above sections involving testing, staff training, and reducing anxiety related to the study will be followed as outlined above.

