**Survey and needs assessment.** The primary source of data collection in all three groups of the study will be from the ACASI questionnaire, administered at 0 months (baseline), 3 months, and 6 months from enrollment. All surveys will be administered on a tablet using the ACHESS application, by the participant accessing the survey in ACHESS on their smartphone or web browser on their own time, or over the phone. The data will be securely stored at UW-Madison and erased from the tablet if

applicable. The survey will consist of multiple choice questions designed to efficiently assess drug use history, access and utilization of prevention services, readiness for intervention, and injection related risk behaviors. The final survey a participant takes will include exit questions to help us evaluate and improve the program. Participants enrolled in the intervention between February 1, 2023 and March 31, 2023 will complete the baseline and 3 months ACASI questionnaire only.

**ACHESS.** All participants will complete study assessments using the ACHESS application. ACHESS can be accessed by downloading the application to a smartphone or via a web browser. Participants may also take part in optional non-research activities within the ACHESS app. These activities include: 1) posting on discussion boards, 2) utilizing the private message function to communicate with study staff or other participants, 3) viewing local community resources and their contact information, 4) viewing and saving motivational quotes of the day and logging thoughts of gratitude, and 5) accessing study staff contact information.

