## **D. Protection of Incarcerated Individuals**

For Aim 3, our program is a 12-week intensive case-management program. Therefore we want to ensure that participants who become incarcerated have a way to re-engage with the study and intervention once they are released from jail or prison. If it is learned that a research participant is incarcerated at any time in the study, they will be immediately un-enrolled and research activities will be suspended. Participants in the intervention arm may receive contact from the prevention navigator to notify them of this and explain the process. No data will be collected from the participant during this time. Upon release, participants may contact Vivent Health staff to re-enroll in the study. The consent document will be reviewed with the participant at this time to re-assess willingness to participate. Participants can take their assessment after 2.5-5.5 months from baseline or follow up assessment. If the opportunity to take the assessment is no longer available, then we treat it as missing.

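### Reminder and scheduling rules for the 3- and 6-month assessments differ by arm, which can cause differential, outcome-related loss in the between-site comparison of self-reported outcomes

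*Combined protocol and SAP*

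**What the plan says.** Section 9.0 H (confidentiality protections) describes follow-up contacts for the two arms in one paragraph.

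- **Intervention arm.** "Vivent Health study staff will perform all follow up contacts with intervention participants". The content is listed: "These follow ups include appointment reminders, appointment scheduling, checking in after an important appointment, booster sessions via phone, and discussing test results". On channel: "These contacts will be made in accordance to the participants' preferred contact method". No maximum is stated.
- **Control arm.** "Contacts with the control group will all be performed by the project manager on the designated study phone". The purpose of the calls is to remind participants to schedule their follow-up visits, and there is a limit: "Control participants will be called no more than 3 times between each research visit to eliminate disruption to their daily lives".

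Appendix 1, section 1.7 gives a different account of control follow-up: syringe service staff at the non-intervention sites recruit participants for the baseline, 3-month and 6-month assessments.

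Comparison B in the same section compares self-reported outcomes between sites with and without navigation. Section 5.4 makes the ACASI questionnaire the main data source. It may be completed on a tablet, "by the participant accessing the survey in ACHESS on their smartphone or web browser on their own time, or over the phone". The person who asks the questions by phone is not named.

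For Aim 3, Section 7.0 plans 270 intervention and 135 control participants for 28% against 42%, with no allowance for loss. Section 6.0 names generalized linear mixed models without a missing-data assumption.

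**The concern.** Comparison B is the only comparison of self-reported outcomes against concurrent controls, and it uses only people who complete a follow-up survey. If the plan is followed as written, the effort to obtain that survey depends on the arm. Loss may then be heavier in the control arm, which is half the size of the other.

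If people who find services easy to reach are also easier to retain, the controls who remain will overstate control access by more than the retained intervention participants overstate theirs, and a real effect shrinks. If the people who remain are those with more unmet need, the error runs the other way. The design is non-randomized and the sponsor already acknowledges its biases. This one is avoidable, and selective loss is hard to repair afterwards.

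**Working it through.** **1. The plan's own figure.** Inputs from Section 7.0: 135 controls at 28%, 270 intervention at 42%. Alpha is 0.05, stated there for Aim 1; two-sided is assumed.

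- Pooled proportion: (135 × 0.28 + 270 × 0.42) / 405 = 0.3733
- SE under the null: √[0.3733 × 0.6267 × (1/135 + 1/270)] = 0.0510
- SE under the alternative: √[0.28 × 0.72/135 + 0.42 × 0.58/270] = 0.0489
- Power: Φ[(0.14 − 1.96 × 0.0510) / 0.0489] = 0.794

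The stated 80% is reproduced, and it assumes that all 405 are analysed. With an assumed 20% loss in both arms, power is 0.697. With 20% loss in the intervention arm and 40% in controls, it is 0.604.

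**2. Bias from unequal retention.** Let p be true access, R overall retention, r1 and r0 retention with and without good access, and OR the retention odds ratio.

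- r1/(1 − r1) = OR × r0/(1 − r0)
- p × r1 + (1 − p) × r0 = R
- Observed access among those retained = p × r1 / R

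The true values 28% and 42% are the plan's. R and OR are assumptions, because the documents give neither. The same OR is applied to both arms.

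Example with OR 2:

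- Controls, R = 0.60: r0 = 0.5556, r1 = 0.7143. Check: 0.28 × 0.7143 + 0.72 × 0.5556 = 0.600. Observed: 0.2000/0.600 = 33.3%.
- Intervention, R = 0.80: r0 = 0.7559, r1 = 0.8610. Check: 0.42 × 0.8610 + 0.58 × 0.7559 = 0.800. Observed: 0.3616/0.800 = 45.2%.
- Difference: 45.2 − 33.3 = 11.9 points, a distortion of −2.1 from the true 14.

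| OR | Control observed (R 60%) | Intervention observed (R 80%) | Distortion | Intervention observed (R 70%) | Distortion |
|---|---|---|---|---|---|
| 1.5 | 31.2% | 43.9% | −1.3 | 44.9% | −0.3 |
| 2 | 33.3% | 45.2% | −2.1 | 46.9% | −0.5 |
| 3 | 36.1% | 46.8% | −3.3 | 49.5% | −0.6 |

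Distortions are in percentage points and come from unrounded values.

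**3. Direction.** Inverting the odds ratios (people with good access are harder to retain) and solving the same equations gives control values of 24.7%, 22.3% and 19.1%. Intervention values at 80% are 40.0%, 38.6% and 36.6%. The distortions become +1.3, +2.2 and +3.6 points. At 70% they are +0.3, +0.6 and +0.9.

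**4. Check under no effect.** With 28% in both arms, equal retention and the same OR, both arms are shifted alike and the bias is zero. With 80% against 60% and OR 2, it is 30.5 − 33.3 = −2.8 points.

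**The case against.** Much can be said for the plan.

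- **Other routes to controls exist.** The cap is on calls. Section 9.0 H also mentions texts: "Phone calls and text messages sent by the UW research team will be performed on a study phone only accessed by one person". No text limit is stated. Controls complete a locator form, those with non-reactive tests leave with a 3-month appointment (Section 5.4), and all participants use ACHESS, which has messaging with study staff. The assessment payments and the optional contact-update payment (Section 9.0 L) are not limited by arm. These reduce the risk but do not make the rules equal.
- **Some intervention contacts are service delivery.** Boosters, check-ins and test results belong to navigation and cannot be equalised. Reminders and scheduling are research contacts and can be. A missing maximum also does not show that contacts will be many.
- **The mixed model may absorb part of the loss**, to the extent that earlier responses predict it. The arithmetic above uses completers at one time point, so it makes no such correction. The plan states no assumption either way.

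Three stronger readings are tempting and are not supported.

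- A reader might set the observed control values (31.2 to 36.1%) against 28% and call the 3.2 to 8.1 points the bias. That ignores selection in the intervention arm. With 60% retention in both arms the controls shift just as much, yet the difference is not reduced; it is 0.7 to 2.1 points too large.
- A reader might infer that navigators ask the phone survey in one arm and the project manager in the other. Section 9.0 H allocates contacts, not survey administration. This is a risk, not a stated procedure.
- Section 9.0 D says "Participants in the intervention arm may receive contact from the prevention navigator to notify them of this and explain the process", which might be read as unequal re-engagement after release. That contact explains un-enrolment. After release the participant makes contact in order to re-enrol, and no staff-initiated contact is described for either arm.

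The remark in Section 9.0 E about phone numbers going out of date justifies a consent waiver for the UG3 cohort. It would apply to both arms and does not show that the cap causes loss.

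**Conclusion.** The concern stands for comparison B. The unequal rule is explicit and covers staff, channel and number of attempts. Under the assumed retention and odds ratios, the planned 14-point difference is distorted by about 0.3 to 3.3 points. The distortion is downward if well-connected people are easier to retain, and of similar size upward if they are harder to retain. Actual retention is unknown, so this range is an illustration and not a forecast.

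Comparison C does not depend on survey retention, and the control-only cap does not touch comparison A. This is a modest, avoidable bias with an inexpensive remedy. It does not invalidate the study.

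**What to change.** In Section 9.0 H, replace the control-only cap with one reminder schedule for research assessments in both arms:

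- the same maximum number of attempts per assessment;
- the same permitted channels, including each participant's preferred method and the locator-form contacts;
- the same role issuing the reminders.

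State that this schedule is separate from navigation contacts such as boosters, check-ins and test results.

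Reconcile Section 9.0 H, where the project manager makes all control contacts, with Appendix 1, section 1.7, where syringe service staff recruit controls for the follow-up assessments.

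As a precaution, state in Section 5.4 that when a survey is done by phone, the same non-navigator research role asks it in both arms.

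The cost is protocol wording and some project-manager time. The downside is slightly more contact burden on controls, which the present cap was meant to limit. A common maximum still respects that aim.
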